8. STUDY ASSESSMENTS AND PROCEDURES

8.1. Administrative and Baseline Procedures

The investigator (or an appropriate delegate at the investigator site) must obtain a signed and dated ICD before performing any study-specific procedures.

Study procedures and their timing are summarized in the [SoA](#). Protocol waivers or exemptions are not allowed.

Adherence to the study design requirements, including those specified in the [SoA](#), is essential and required for study conduct.

All screening evaluations must be completed and reviewed to confirm that potential participants meet all eligibility criteria. The investigator will maintain a screening log to record details of all participants screened and to confirm eligibility or record reasons for screening failure, as applicable.

Participants will be screened within 28 days prior to administration of the study intervention to confirm that they meet the study population criteria for the study. If the time between screening and dosing exceeds 28 days as a result of unexpected delays (eg, delayed drug shipment), then participants do not require rescreening if the laboratory results obtained prior to first dose administration meet eligibility criteria.

A participant who qualified for this protocol but did not enroll from an earlier cohort/group may be used in a subsequent cohort/group without rescreening, provided laboratory results obtained prior to the first dose administration meet eligibility criteria for this study. In addition, other clinical assessments or specimen collections (eg, retained research samples) may not need to be repeated, as appropriate.

A participant who qualified for this protocol, completed Day -1 procedures and assessments, and was not dosed as one of the first 2 sentinel participants in a period may be dosed after the study required minimum 24-hour pause without repeating Day -1 procedures and assessments as long as no more than 48 hours separate Day -1 and Day 1. In addition, other clinical assessments or specimen collections (eg, retained research samples) may be used without repeat collection, as appropriate.

Every effort should be made to ensure that protocol-required tests and procedures are completed as described. However, it is anticipated that from time to time there may be circumstances outside the control of the investigator that make it unfeasible to perform the test. In these cases, the investigator must take all steps necessary to ensure the safety and well-being of the participant. When a protocol-required test cannot be performed, the investigator will document the reason for the missed test and any corrective and preventive actions that they have taken to ensure that required processes are adhered to as soon as possible. The study team must be informed of these incidents in a timely manner.

Any safety, laboratory, or analyte results that have been collected for the purposes of this study and could unblind the study will not be reported to investigative sites or other blinded personnel until the study has been unblinded.

If done around the time of a blood draw, ECGs and vital sign assessments (BP and pulse rate) should be collected before the blood draw.

If an IV catheter is utilized for blood sample collections, ECGs and vital sign assessments (pulse rate and BP) should be collected prior to the insertion of the catheter.

For samples being collected and shipped, detailed collection, processing, storage, and shipment instructions and contact information will be provided to the investigator site prior to initiation of the study.

The total blood sampling volume for individual participants in this study is approximately 400 mL. The actual collection times of blood sampling may change. Additional blood samples may be taken for safety assessments at times specified by Pfizer, provided the total volume taken during the study does not exceed 550 mL during any period of 56 consecutive days.

To prepare for study participation, participants will be instructed on the information in the [Lifestyle Considerations](#) and [Prior and Concomitant Therapy](#) sections of the protocol.

8.2. Efficacy Assessments

Efficacy parameters are not evaluated in this study.

8.3. Safety Assessments

Planned time points for all safety assessments are provided in the [SoA](#). Unscheduled safety measurements may be obtained at any time during the study to assess any perceived safety issues.

8.3.1. Physical Examinations

A complete PE will include, at a minimum, head, ears, eyes, nose, mouth, skin, heart and lung examinations, lymph nodes, and gastrointestinal, musculoskeletal, and neurological systems.

A brief PE will include, at a minimum, assessments of general appearance, the respiratory and cardiovascular systems, and participant-reported symptoms.

PEs may be conducted by a physician, trained physician's assistant, or nurse practitioner as acceptable according to local regulation.

Height and weight will also be measured and recorded as per the [SoA](#). For measuring weight, a scale with appropriate range and resolution is used and must be placed on a stable, flat surface. Participants must remove shoes, bulky layers of clothing, and jackets so that only light clothing remains. They must also remove the contents of their pockets and remain still during measurement of weight.

Physical examination findings collected during the study will be considered source record and will not be required to be reported, unless otherwise noted. Any untoward physical examination findings that are identified during the active collection period and meet the definition of an AE or SAE ([Appendix 3](#)) must be reported according to the processes in [Sections 8.4.1 to 8.4.3](#).

8.3.2. Neurological Examinations

Neurological examinations may be conducted by a physician, trained physician's assistant, or nurse practitioner as acceptable according to local regulation at the nominal time points specified in the [SoA](#). The neurological exam will consist of assessment of higher cortical function, the cranial nerves, motor function, deep tendon reflexes, sensory exam, and coordination and gait. Additional neurological examinations that are outside of [SoA](#) (eg, to evaluate an AE) may be conducted at the discretion of investigator. All neurological exams should be done to the extent needed to assess the participant for any potential changes in neurological status, as determined by the investigator (or designee). Changes in the timing or addition of timepoints for the neurological examinations may occur based on emerging data.

8.3.3. Vital Signs

8.3.3.1. Blood Pressure and Pulse Rate

Supine BP will be measured with the participant's arm supported at the level of the heart and recorded to the nearest mm Hg after approximately 5 minutes of rest. The same arm (preferably the dominant arm) will be used throughout the study. Participants should be instructed not to speak during measurements. When triplicate measurements of supine BP or pulse rate are required per [SoA](#), measurements should be collected 2-4 minutes apart.

The same properly sized and calibrated BP cuff will be used to measure BP each time. The use of an automated device for measuring BP and pulse rate is acceptable; however, when done manually, pulse rate will be measured in the brachial/radial artery for at least

30 seconds. When the timing of these measurements coincides with a blood collection, BP and pulse rate should be obtained prior to the nominal time of the blood collection.

Additional collection times, or changes to collection times, of BP and pulse rate will be permitted, as necessary, to ensure appropriate collection of safety data.

Any untoward vital sign **findings** that are identified during the active collection period and meet the definition of an AE or SAE ([Appendix 3](#)) must be reported according to the processes in [Sections 8.4.1 to 8.4.3](#).

8.3.3.2. Respiratory Rate

Respiratory rate will be measured after approximately 5 minutes rest in supine position by observing and counting the respirations of the participant for 30 seconds and multiplied by 2. When BP is to be taken at the same time, respiration measurement will be done during the 5 minutes of rest and before BP measurement.

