Potential Risk of Clinical Significance	Summary of Data/Rationale for Risk	Mitigation Strategy
Study Intervention(s) PF-07853578		
	glands was seen in female and male rats.	
Effects on the liver	Non-adverse increases in liver weight and hepatocyte hypertrophy were seen in rats, and increased ALT in female dogs with PF-07853578 in 14-day GLP toxicology studies.	
Serial liver function tests will be measured as part of standard clinical safety labs.
Effects on pulmonary function	CCI [REDACTED] were seen in rats with PF-07853578 in single-dose safety pharmacology studies.	
Respiratory rate will be assessed serially as part of safety monitoring.

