9.3.1. Safety Analyses

All safety analyses will be performed on the safety population (safety analysis set).

AEs, ECGs, BP, pulse rate, continuous cardiac monitoring, and safety laboratory data will be reviewed and summarized on an ongoing basis during the study to evaluate the safety of participants. Any clinical laboratory, ECG, BP, pulse rate, and respiratory rate abnormalities of potential clinical concern will be described. Safety data will be presented in tabular and/or graphical format and summarized descriptively, where appropriate.

Medical history and physical examination and neurological examination information, as applicable, collected during the course of the study, will be considered source data and will not be required to be reported, unless otherwise noted. However, any untoward findings identified on physical and/or neurological examinations conducted during the active collection period will be captured as AEs, if those findings meet the definition of an AE.

Data collected at screening that are used for inclusion/exclusion criteria, such as laboratory data, ECGs, and vital signs, will be considered source data, and will not be required to be reported, unless otherwise noted. Demographic data collected at screening will be reported.

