3.1.3. Vital Signs

Single supine blood pressure and pulse rate measurements will be taken at screening, follow-up visit and at early termination (if applicable). Triplicate supine measurements will be taken at all other times as detailed in the Schedule of Activities (SoA) in the protocol. The average of the triplicate measurements will be calculated prior to analyzing the data. Respiratory rate will be measured at each timepoint specified in the protocol.

Baseline for these measures will be defined as the last pre-dose measurement in each study period.

The following endpoints will be determined:

- Change from baseline (CFB) in systolic and diastolic BP, pulse rate and respiratory rate
- The minimum and maximum post-dose systolic and diastolic BP, pulse rate and respiratory rate
- The maximum increase and decrease from baseline over all measurements taken postdose for systolic and diastolic BP, pulse rate and respiratory rate values

The maximum decrease and increase from baseline over all measurements taken post-dose will be calculated for supine systolic and diastolic blood pressures and pulse rates. The maximum increase from baseline will be calculated by selecting the maximum change from baseline over the respective period, except in the case where a participant does not show an increase. In such an instance, the minimum decrease should be taken. Similarly, the maximum decrease from baseline will be determined by selecting the minimum value of the change from baseline. In cases where a participant does not show a decrease, the minimum increase should be taken.

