6.1.3. Vital Signs

Absolute values and changes from baseline (as defined in Section 4) in supine systolic and diastolic blood pressure, respiratory rate, and pulse rate will be listed, and summarized by dose and treatment (if applicable) and time point, according to sponsor reporting standards using the safety population defined in Section 4.

Mean absolute values and mean changes from baseline for systolic and diastolic blood pressure, respiratory rate, and pulse rate will be plotted against time point. On each plot, there will be 1 line for each treatment with all treatments on the same plot. Corresponding individual plots of changes from baseline will also be produced for each treatment.

Maximum and minimum absolute values and changes from baseline (as defined in Section 3.1) for supine vital signs will also be summarized descriptively by dose and treatment (if applicable) using categories as defined in Appendix 2.

Numbers and percentages of participants meeting the categorical criteria will be provided. All planned and unplanned post dose time points will be counted in these categorical summaries. All values meeting the criteria of potential clinical concern will be listed.

Values meeting the categorical criteria occurring pre-dose on Day 1 for each period starting with Period 2, will be attributed to the treatment from the previous period (e.g., for cohort 1, an occurrence pre-dose at Period 2 Day 1 will be attributed to the Period 1 dose).

Data collected at screening that are used for inclusion/exclusion criteria, will be considered source data, and will not be required to be reported, unless otherwise noted.

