Appendix 1. PK Analyses – Example of SAS Code for mixed effects model

An example of the PROC MIXED code:

proc mixed data=tab.pk;
 class trt subject;
 model &var = trt / ddfm=KR;
 random subject /subject=subject;
 lsmeans trt/ diff cl alpha=0.1;
run;

Appendix 2. Categorical Classes for ECG and Vital Signs of Potential Clinical Concern Categories for QTcF

Absolute value of QTcF (msec)	>450 and ≤480	>480 and ≤500	>500
Increase from baseline in QTcF (msec)	>30 and ≤60	>60	

Categories for PR and QRS

PR (msec)	max. ≥300	
PR (msec) increase	Baseline >200 and	Baseline ≤200 and
	max. ≥25% increase	max. ≥50% increase
QRS (msec)	max. ≥140	
QRS (msec) increase from baseline	≥50% increase	

Categories for Vital Signs

Systolic BP (mm Hg)	min. <90	
Systolic BP (mm Hg) change from baseline	max. decrease ≥30	max. increase ≥30
Diastolic BP (mm Hg)	min. <50	
Diastolic BP (mm Hg) change from baseline	max. decrease ≥20	max. increase ≥20
Supine pulse rate (bpm)	min. <40	max. >120

Measurements that fulfill these criteria are to be listed in the report.

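### Respiratory rate, the only mitigation listed for the pulmonary risk, is a 30-second count doubled, and no pre-specified rule in the protocol or SAP flags a value as of potential clinical concern

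*Protocol*

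**What the plan says.** **Why the measurement is taken.** The pulmonary row of the table in protocol 2.3.1 refers to findings in rats from single-dose safety pharmacology studies; their nature is redacted. The one mitigation in that row is: "Respiratory rate will be assessed serially as part of safety monitoring".

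**How it is taken.** Protocol 8.3.3.2 has the participant rest supine for about 5 minutes. The rate is then obtained "by observing and counting the respirations of the participant for 30 seconds and multiplied by 2". The Schedule of Activities and SAP 3.1.3 require in-period blood pressure and pulse rate in triplicate. Neither states replication for respiratory rate.

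**What the protocol says will be reported.** Section 9.3.1: "Any clinical laboratory, ECG, BP, pulse rate, and respiratory rate abnormalities of potential clinical concern will be described".

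**What the SAP does with it.**
- Section 3.1.3 defines change from baseline, "The minimum and maximum post-dose systolic and diastolic BP, pulse rate and respiratory rate", and the maximum increase and decrease from baseline.
- Section 6.1.3 lists, summarizes and plots values and changes by time point, respiratory rate included.
- The same section says that maximum and minimum values and changes for supine vital signs will be "summarized descriptively by dose and treatment (if applicable) using categories as defined in Appendix 2", and adds: "All values meeting the criteria of potential clinical concern will be listed".
- In Appendix 2, the table under "Categories for Vital Signs" has rows for systolic BP, diastolic BP and supine pulse rate only.
- Section 2.1 declares no modification of the protocol's analysis plan.

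**The concern.** There are two separate issues.

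**Resolution.** Doubling a 30-second count means only even values can be recorded. With about 6 active and 2 placebo participants per dose level, a small respiratory effect has to be read from few, coarse readings. The protocol ties this vital sign to a named nonclinical risk, so a cheap gain in precision is worth considering.

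**Flagging.** The extreme-value endpoints for respiratory rate are sent to a set of categories that does not include it. Blood pressure and pulse have pre-specified limits; the vital sign attached to the pulmonary risk has none. If a limit is chosen later, in a study where a sponsor team sees unblinded data as it accrues, the choice can be influenced by the data. If none is chosen, what counts as an abnormality to be described under protocol 9.3.1 rests on judgment alone.

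**Working it through.** The plan states no precision, power or threshold for respiratory rate, so there is no figure of its own to reproduce.

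**1. Step size.** A count over T seconds gives steps of 60/T breaths/min.
- 30 seconds: 60/30 = 2/min.
- 60 seconds: 60/60 = 1/min.
- At assumed resting rates of 12, 16 and 20/min, a step of 2 is 16.7%, 12.5% and 10.0% of the value.

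**2. Rounding error alone.** Assume perfectly regular breathing with a random starting phase. With f the fractional part of the expected count, one reading has SD (60/T)·√(f(1−f)). Averaged over f, this is (60/T)·√(1/6). A change from baseline multiplies it by √2, and a mean over 6 participants divides it by √6.

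| Count | SD, one reading | SD, change from baseline | SE, mean change, n = 6 |
|---|---|---|---|
| 30 s | 2 × 0.408 = 0.82 | 1.15 | 0.47 |
| 60 s | 1 × 0.408 = 0.41 | 0.58 | 0.24 |

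The worst case for 30 seconds (f = 0.5) is SD 1.0 for one reading, 1.41 for a change and SE 0.58 for the mean of 6. For group means the rounding error is small. It matters more for one participant's change of about 2/min.

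**3. Irregular breathing added.** Breath intervals were simulated as gamma-distributed with a random start. The CV of 20% is an assumption. The measurement SDs (breaths/min) were:

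| True rate | 30 s | 60 s |
|---|---|---|
| 12/min | 1.28 | 0.80 |
| 14/min | 1.34 | 0.85 |
| 16/min | 1.40 | 0.90 |

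A biological SD of 1.5/min per reading, also assumed, is then added: SD of change = √(2·(SD² + 1.5²)). At 14/min:
- 30 s: √(2·(1.34² + 1.5²)) = √8.09 = 2.84.
- 60 s: √(2·(0.85² + 1.5²)) = √5.95 = 2.44.
- Reduction: 1 − 2.44/2.84 = 14%.

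The same formula gives 14% at 12/min (2.79 to 2.40) and 15% at 16/min (2.90 to 2.47). Over CV 10–30% and biological SD 1–2/min the reduction is about 6–24%. It is smallest when breathing is regular and biological variation large, and largest in the opposite case. A repeat of the simulation reproduced these figures to within rounding.

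**4. The flagging route, followed as written.**

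| Step | Systolic BP, diastolic BP, pulse | Respiratory rate |
|---|---|---|
| Abnormalities to be described (protocol 9.3.1) | Yes | Yes |
| Minimum, maximum and maximum change defined (SAP 3.1.3) | Yes | Yes |
| Values and changes listed, summarized, plotted (SAP 6.1.3) | Yes | Yes |
| Category in SAP Appendix 2 | Yes | None |
| Flagged or listed as of potential clinical concern by rule | Possible | Not possible |

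Protocol Appendix 8 gives criteria for ECG findings only, so it does not fill the gap. SAP 3.1.3 is also uneven within itself. Its bullets include respiratory rate among the maximum-change endpoints, but the paragraph explaining how to calculate them names only blood pressure and pulse rate.

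**The case against.** **The count is not a defect.** A 30-second count contradicts nothing in the documents, and protocol 8.3.3.1 accepts at least 30 seconds for a manual pulse. This stands: a longer count is an improvement, not a correction.

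**The gain rests on assumed variances.** Neither the breath-interval CV nor the biological SD is in the documents. This stands, and is why a range is given. A reader might turn the 14/min case into a sample-size equivalent: (2.84/2.44)² ≈ 1.35, or about 35% more participants. The documents do not support using it that way. Protocol 9.1 plans no hypothesis test, and 9.5 does not base the sample size on precision.

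**Respiratory rate is not ignored.** A reader might infer from Appendix 2 that no respiratory value will be listed at all. SAP 6.1.3 shows otherwise: values and changes are listed, summarized and plotted, with individual plots. What is missing is only the rule that marks a value as of concern.

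**Other safeguards exist.** A reader might also infer that nothing else monitors respiration. That is true only of the risk-table row. Physical examinations cover the lungs or respiratory system (protocol 8.3.1), unscheduled measurements are allowed (8.3), and untoward vital-sign findings that meet the AE definition must be reported (8.3.3.1). These rely on judgment and do not supply a criterion.

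**Protocol 9.3.1 promises description, not categories.** Laboratory abnormalities, named in the same sentence, also have no Appendix 2 row. But SAP 3.1.2 expressly sends them to criteria in the sponsor reporting standards. SAP 6.1.3 cites those standards for the summaries of vital signs, and they may hold a respiratory-rate limit. The documents do not show one, and 6.1.3 names Appendix 2 as the source of the categories.

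**Adequacy cannot be judged.** The rat finding is redacted, so its direction and size are unknown. This stands: nothing here shows that steps of 2/min would miss a relevant effect.

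**Conclusion.** The point holds as a low-severity improvement in two parts.

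The counting method is workable but coarser than it needs to be. A 60-second count halves the step from 2 to 1/min and reduces the SD of change from baseline by about 14–15% at 12–16/min (assumed CV 20%, biological SD 1.5/min), or about 6–24% over the wider assumptions. Only the step size is independent of assumptions.

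The SAP gap is a matter of text and needs no assumption. Extreme-value endpoints for respiratory rate are defined in SAP 3.1.3 and sent by 6.1.3 to Appendix 2, which has no category for them. Protocol 9.3.1 can still be met by judgment, and the data will be visible in listings and plots. It cannot be met through a pre-specified rule found in either document. If the sponsor standard contains one, the defect shrinks to a missing citation.

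**What to change.** 1. In protocol 8.3.3.2, change the count to a full 60 seconds, without multiplication, within the supine rest already required.
2. Reconcile SAP 3.1.3, 6.1.3 and Appendix 2 with protocol 9.3.1. Add respiratory-rate rows to Appendix 2 (absolute low and high, and change from baseline), with limits set by the sponsor's clinicians before first dosing. Alternatively, cite the sponsor reporting standard that contains them. No limit can be derived from these documents and none is proposed here.
3. In SAP 3.1.3, name respiratory rate in the paragraph that explains how maximum increases and decreases are calculated.

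**Cost.** Thirty more seconds per reading, with no added visit, staff or procedure. Item 1 changes protocol text, so it needs an amendment with the review that protocol 10.1.1 requires, and could be combined with other changes. Items 2 and 3 need two table rows (or a citation) and a few words in the SAP.

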8.3.4. Electrocardiograms

Standard 12-lead ECGs will be collected at times specified in the [SoA](#) section of this protocol using an ECG system that automatically calculates the HR and measures PR, QT, QTcF, and QRS intervals. All scheduled ECGs should be performed after the participant has rested quietly for at least 5 minutes in a supine position.

Triplicate 12-lead ECGs will be obtained approximately 2-4 minutes apart; the average of the triplicate ECG measurements collected at -1.0, -0.5, and 0 hours pre-dose on Day 1 of each period will serve as each participant's baseline QTcF value for that period.

To ensure safety of the participants, a qualified individual at the investigator site will make comparisons to baseline measurements from the current period. Additional ECG monitoring will occur if a) the mean value from the triplicate measurements for any post-dose QTcF interval is increased by ≥ 60 ms from the baseline **and** is > 450 ms; or b) an absolute QT value is ≥ 500 ms for any scheduled ECG. If either of these conditions occurs, then a single ECG measurement must be repeated at least hourly until QTcF values from 2 successive ECGs fall below the threshold value that triggered the repeat measurement.

For single ECG collections, additional ECG monitoring will occur if a) a postdose QTcF interval is increased by ≥ 60 ms from the baseline **and** is > 450 ms; or b) an absolute QT value is ≥ 500 ms for any scheduled ECG. If either of these conditions occurs, then 2 additional ECGs will be collected approximately 2 to 4 minutes apart to confirm the original measurement. If the QTcF values from these repeated ECGs remain above the threshold value, then a single ECG must be repeated at least hourly until QTc values from 2 successive ECGs fall below the threshold value that triggered the repeat measurement.

If a) a postdose QTcF interval remains ≥ 60 ms from the baseline **and** is > 450 ms; or b) an absolute QT value is ≥ 500 ms for any scheduled ECG for greater than 4 hours (or sooner, at the discretion of the investigator); or c) QTcF value get progressively longer, the participant should undergo continuous ECG monitoring. A cardiologist should be consulted if QTcF

values do not return to less than the criteria listed above after 8 hours of monitoring (or sooner, at the discretion of the investigator).

In some cases, it may be appropriate to repeat abnormal ECGs to rule out improper lead placement as contributing to the ECG abnormality. It is important that leads be placed in the same positions each time in order to achieve precise ECG recordings. If a machine-read QTc value is prolonged, as defined above, repeat measurements may not be necessary if a qualified medical provider's interpretation determines that the QTcF values are in the acceptable range.

ECG values of potential clinical concern are listed in [Appendix 8](#).

